4.6 Screen Failures

For all screen failures, information including demography, screen failure details, and eligibility criteria will be collected. Re-screening generally will be considered after ≥ 1 month and/or at the discretion of the Lead PI, Site-PI, and study team depending on reason for screen failure.

4.7 Participant Withdrawal Criteria

4.7.1 When and How to Withdraw Participants

Patient participants are free to withdraw from participation in the clinical trial at any time. Completion of the study visits involving doing self-report surveys or semi-structured interviews do not have any withdrawal criteria except clinical instability precluding them from safely engaging in the assessment, as determined by the Lead PI/Site-PI.

For the Week1, accelerated deep TMS treatment period: An investigator will discontinue or withdraw a participant for the following reasons:

- Requires in-patient psychiatric hospitalization.
- Develops clinically significant hypomanic or manic symptoms. Possible hypomanic or manic syndromes may be identified by study staff and a study physician will be immediately notified to conduct an assessment.
- Cannot tolerate stimulation at 90% RMT on ≥ 5 treatment sessions overall.
- Develops any medical illness that may be unstable or experience a seizure.
- If a participant must miss rTMS treatments because of COVID-19 symptom screening/exposure restrictions and are not allowed to be on-site, those sessions will not count towards having to discontinue from study treatment per withdrawal criteria. It will be at the discretion of the investigators on a case-by-case basis if a participant needs to discontinue treatment during the trial should the absence secondary to COVID-19 symptom restrictions be prolonged.

For the entire study period: An investigator may discontinue or withdraw a participant for the following reasons:

- Pregnancy
- Withdraws consent.

- Meets an exclusion criterion (either newly developed or not previously recognized) related to safety that precludes further treatment.
- Demonstrates clinical instability to the point where further participation in the study would not be in the best interests of the participant, at the discretion of the PI and the study investigator team.

The reason for participant discontinuation or withdrawal from the study will be recorded within the participant's research record, and/or legal health record. Data up to the point of their last visit may be included in the analysis.

4.7.2 Follow-up for Withdrawn Participants

If a participant withdraws consent, they can also request the withdrawal of their data subject to any research-specific restrictions, unless the data has already been de-identified and shared. Once withdrawn from the clinical trial, no further research procedures or evaluations will be performed, or additional research-specific data collected on the participant. Reasonable effort will be made to obtain permission to document the reason for withdrawal.

4.7.3 Early Termination Visit

If a patient participant withdraws from the clinical trial, they will be asked to attend an Early Termination Visit. This includes all assessments included in the post rTMS treatment visit as well as:

- Assessment of new and ongoing AEs.
- Assessment of any complications following the study intervention.
- Documentation of all concomitant medications.

The PI will ensure the participant is appropriately followed for any additional care as required. Data collected until the time of withdrawal may be used in analyses.

4.7.4 Participants who are Lost to Follow-up

A patient participant will be considered lost to follow-up if they fail to return for >3 scheduled visits that cannot be rescheduled and are unable to be contacted by the research team.

The following actions will be taken if a participant fails to attend a required study visit:

- The research team will attempt to contact the participant and reschedule the missed visit within the next 4 weeks and reconfirm whether the participant wishes to and/or should continue in the study.

- Before a participant is deemed lost to follow-up, the research team will make every effort to regain contact with the participant (where possible, at least five contact attempts including both telephone calls and emails, unless specific contact preferences were specified by the participant). These contact attempts will be documented in the participant's research record and/or legal health record.
- Should the participant continue to be unreachable, they will be considered to have withdrawn from the clinical trial with a primary reason of lost to follow-up. Data up to the point of their last visit will be included in the analysis.

5.0 STUDY INTERVENTION

5.1 Description

Treatment will be delivered through the H4 coil (Brainsway, Israel) and Brainsway stimulator system, generally following previously established reports[41]. Week 1, the treatment period, will begin on the participant's Target Quit Date (TQD), which will be standardized to coincide with the first day of TMS, as smokers are believed to be most susceptible to relapse during the early abstinence phase[61]. However, this may vary due to scheduling constraints. Resting motor threshold (RMT) will be established to determine stimulation intensity at the beginning of the treatment course. This is obtained by finding the optimal position of the helmet that elicits reliable activation of the right abductor pollicis brevis muscle, before then aligning the helmet symmetrically and moving it 6 cm anteriorly. Titration of stimulus intensity may occur to enhance tolerability. Stimulation intensity will be set at 120% RMT, with a minimum of 90% RMT if there are issues with tolerability. Initial sessions may start at a lower intensity (approximately 70% RMT) and increase accordingly. Sixty trains of 30 pulses each (total 1,800 pulses) will be applied at 10 Hz, for 3 second trains, with a 15 second inter-train interval, for approximately 18 minutes of treatment time. For each day within Week 1, four sessions will be administered, with an intersession interval of 30 minutes. TMS could be reschedule the next week in case of holidays, hospital closure or other factors that prevent booking the subjects.

Participants will be asked to abstain from smoking for ≥ 2 hours before each visit in Week 1. Before the first session of each day in Week 1, it will be preceded by a brief provocation procedure that involves participants being asked to imagine one of their biggest triggers for smoking cravings, viewing pictures of smoking and handling a cigarette and lighter (with no lighter fluid) guided by a scripted recorded voice. In their baseline clinical assessment, participants will identify a list of their top 5 triggers for smoking. For the first session of each day in Week 1, prior to stimulation, first the participant will be asked to close their eyes and imagine one of the identified triggers for 30 seconds. Next they will be presented with real cigarettes and a lighter, and then be asked to listen to a recording for how to handle a cigarette and a lighter for 2 minutes. The recording will tell the participant to hold both items; they will not be asked to light the cigarette or smoke the cigarette. The cigarette and lighter will be as similar as

possible to what each individual participant usually uses. If possible, the lighter fluid will be removed from the lighter to reduce fire risk. Following this, they will watch a PowerPoint presentation of smoking pictures for 2 minutes and 30 seconds. Thus, the entire procedure will be 4 minutes prior to stimulation start administered by trained research staff.

5.2 Treatment Regimen

The treatment course consists of daily treatment with four sessions per day, over five days in Week 1 (one week), for a total of 20 treatment sessions.

5.3 Method for Assigning Participants to Treatment Groups

Since this is a one-arm trial, all participants will receive accelerated deep TMS, with no randomization or allocation to different groups.

5.4 Administration of Study Intervention

Deep TMS with accelerated protocol: Each treatment will be administered by an rTMS technician, RPN, or other trained individual. The individual responsible for administering all treatments will be adequately trained through the Sunnybrook Research Institute and Waypoint Centre for Mental Health Care, in collaboration with the University of Toronto, which offers a successful rTMS technician course covering all the technical and hands-on training required for the safe and effective delivery of rTMS.

Each day in Week 1 will last approximately 3 hours including 4 minutes for general setup, 3 minutes for the cue-induced craving protocol, and four 18-minute rTMS sessions interleaved with three 30-minute intervals approximately (4-3-18-30-18-30-18-30-18). Scheduling may vary slightly based on equipment availability.

5.5 Participant Compliance Monitoring

Attendance to rTMS treatment sessions will be tracked and missed sessions will be counted. Any withdrawal from the study due to non-compliance will be addressed as per section 4.7.

5.6 Concomitant Therapy

All prescribed medications, over-the-counter medications, and supplements will be recorded and reviewed by the Lead PI/Site-PI at screening/baseline. Concomitant

medications and therapies will be verified with research participants at each study visit. All participants will have the opportunity to discuss their concomitant medications, and the risks and benefits of the study intervention will be reviewed with the study doctor (see Section 4.4.2: Patient Participant Exclusion Criteria).

Currently, no pharmacological agents have been shown to have any clear interactions (whether beneficial or harmful) with rTMS. Participants will be informed that the pilot and pivotal RCTs supporting the use of deep TMS for smoking cessation also excluded individuals already using other smoking cessation treatments. Therefore, participants will be asked not to initiate any new medications intended to aid smoking cessation during the 13-week study course, as outlined in Section 4.4.2.

As mentioned in Section 4.5: Lifestyle Considerations, reducing cigarette smoking may alter the levels of certain medications due to its effects on CYP1A2 metabolism. Additionally, smoking reduction may impact insulin resistance and glycemic control in individuals with diabetes. In such cases, medications metabolized by CYP1A2 or those used for diabetes management may require dose adjustments at the discretion of the study physician and the prescribing physician.

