3.0 CLINICAL TRIAL DESIGN

3.1 Overall Design

This clinical trial is designed as a one-arm, open-label study to evaluate the efficacy and feasibility of the H4 deep accelerated transcranial magnetic stimulation (aTMS) protocol for smoking cessation. The absence of a control group is intentional, as this pilot study focuses on assessing the intervention's preliminary efficacy in a single arm of 40 participants with tobacco use disorder who are motivated to quit, aiming for 30 completers to guide a future controlled trial. Each participant's involvement will last 26 weeks, starting with a screening phase at Week 0, followed by a one-week treatment period in Week 1, and concluding with follow-up visits at Weeks 3, 5, 9, 13, and 26. The entire trial is expected to span approximately 2 years, covering recruitment, treatment, and follow-up for all participants.

During Week 1, participants will receive 20 rTMS sessions using the Health Canada-approved H4 deep TMS coil, administered at four sessions per day over five consecutive days, targeting the insular cortex, alongside brief counseling adapted from the Mayo Clinic's 'Smoke Free and Living It' manual. Daily assessments will monitor safety, Timeline Followback (TLFB), and nicotine craving and withdrawal symptoms. The primary outcome is overall feasibility, including measures of tolerability, acceptability, retention, and adherence. Secondary outcomes include 7-day point prevalence abstinence—verified by self-report and urine cotinine levels (<200 ng/mL)—at the end of treatment and at Weeks 3, 5, 9, 13, and 26. We will also assess 3-month abstinence at Week 13 and 6-month abstinence at Week 26, both verified by continuous self-reported abstinence during

the respective periods and corresponding urine cotinine levels. Factors such as comorbidities, pre-existing tobacco use disorder severity, or motivation level for abstinence may influence results; these are addressed through eligibility criteria and statistical adjustments.

It is anticipated that a proportion of enrolled participants may not proceed to the treatment phase (Week 1) due to scheduling, logistical, or personal factors. These individuals will be classified as early dropouts and excluded from the intent-to-treat analysis, which will include only participants who initiate at least one TMS session.

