3.3 Secondary Endpoints

1. Proportion of participants achieving 7-day point prevalence abstinence at end of treatment, Week 3, Week 5, Week 9, Week 13, and Week 26.
2. Proportion of participants achieving prolonged and continuous abstinence at Week 13 and Week 26.
3. Change in self-reported craving, average cigarettes smoked per day, and dependence severity (e.g., using standardized questionnaires) from baseline through study completion.

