4.4.2 Exclusion Criteria

An individual who meets any of the following criteria will be excluded from participation in this clinical trial:

1. Reported smoking abstinence in the 3 months preceding screening visit;
2. Current use of other smoking cessation aids;
3. Contraindication to rTMS;
4. Pregnancy, trying to become pregnant or breastfeeding;
5. Current or recent history of cerebrovascular disease;
6. Unstable major psychiatric disorder(s) (i.e. Axis I Disorders) that would prevent participation in the study at PI (or its delegate) discretion;
7. Serious current or personal history of medical condition/disease (neurological disorders, brain lesions, multiple sclerosis, head trauma, loss of consciousness, hearing loss, etc.) preventing same inclusion as per PI (or its delegate) discretion;
8. Current, personal history or family history of seizures;
9. Concomitant use of medication that lowers seizure threshold, such as clozapine;
10. Concomitant use of more than 2 mg lorazepam (or an equivalent) or any anticonvulsants.

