Follow-up period (Week 13 and 26)

During the Week 13 and 26 visit, a urine cotinine test and TLFB will be administered to determine prolonged abstinence and continuous abstinence. Three-month or six-month prolonged abstinence is defined as abstinence from the end of treatment (W1D5) to the end of follow-up (Week 13 or 26), while three-month or six-month continuous abstinence is defined as abstinence from the target quit day (in Week 1) to the end of follow-up (Week 13 or 26). Assessments for nicotine dependence, withdrawal, craving, and symptoms of depression, anxiety, and mania will also be performed.

- Concomitant medication log, recorded by its generic name, dosage, and dosing frequency
- Timeline Follow-Back (TLFB) – Amount of cigarette used every day since the last follow-up
- Fagerstrom Test of Nicotine Dependence (FTND). The FTND is a measure of physical dependence severity.
- Tobacco Craving Questionnaire-Short-Form (TCQ-SF), to measure smoking craving.
- Minnesota Nicotine Withdrawal Scale (MNWS), to measure the nicotine withdrawal symptoms.
- Patient Health Questionnaire (PHQ-9), to track the possible effects of TMS on depression symptoms.

- General Anxiety Disorder-7 (GAD-7), to track the possible effects of TMS on anxiety symptoms.
- Altman Self-Rating Mania Scale (ASRM), to track the possible effects of TMS on developing manic/hypomanic symptoms
- Adverse event log
- Urine cotinine test (threshold: 200 ng/ml)
- Brief counseling for smoking cessation, adapted from the Mayo Clinic's 'Smoke Free and Living It' manual.

All assessments and surveys during research visits can be completed in one of two ways, based on participant preferences or each site's standard data collection practices:

1. **Paper option:** Assessments and surveys printed from REDCap will be completed by hand. A study delegate will review the paper source for completeness and accuracy and enter the data into REDCap.
2. **Electronic:** A study delegate will log into REDCap and will remain present while the participant enters their responses to assessments on an electronic device (e.g., computer, iPad). The study delegate will review the assessment for completeness before saving and help the participant navigate to the next assessment or survey, as necessary.

Procedures for addressing active suicidal ideation during research visits can be found in [Section 8.5 \(Safety Management Plan\)](#).

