7.2 Statistical Methods

Descriptive statistics will be used to summarize the baseline clinical and demographic variables for the study population. Subjects with missing values will be compared with completers on baseline characteristics, to help in the understanding of the reasons for missing values, if at least 10 subjects (25%) are found to be missing.

For the abstinence measure, an intent-to-treat (ITT) approach will be used, including all participants who received at least one TMS session, regardless of treatment completion.

Mixed effect logistic regression, using abstinence at the end of treatment, Week 3, Week 5, Week 9, Week 13, and Week 26 as dependent variables will be adjusted to the data. Categorical time points (end of treatment and Week 3, Week 5, Week 9, Week 13 and Week 26) will be specified as fixed effect, and subject intercepts as random effects. Baseline variables correlated with missingness and/or known to be associated with the outcome will be added as covariates, with focus on model parsimony (not to include many covariates) due to small sample size. Abstinence will be analyzed at the end of treatment, Week 3, Week 5, Week 13, and Week 26 as part of our secondary objectives.

Mixed effect models using maximum likelihood estimation accounts for missingness in the dependent variable by using all available information in the estimation, under the MAR assumption (Missing At Random – the values of a data points are not associated with the missing status of the data point after accounting for relevant covariates)[1]. Other measures related to our secondary objectives (e.g., FTND, TLFB, etc.) will also be analyzed using linear mixed or generalized mixed models, depending on the nature of the outcome of interest. Graphs will be used to explore the data, the models assumptions (for example, residual plots), as well as model results (for example, estimated means plot).

Due to small sample, effect sizes with 95% confidence intervals as well as standardized effect sizes will be reported.

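### Section 5.6 limits the request not to start cessation medication to a 13-week study, but the study runs 26 weeks and abstinence is assessed at Week 26

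*Protocol*

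**What the plan says.** Section 5.6 (Concomitant Therapy) explains that the trials supporting deep TMS for smoking cessation left out people already on other cessation treatments. It concludes that "participants will be asked not to initiate any new medications intended to aid smoking cessation during the 13-week study course", and refers to Section 4.4.2 for this.

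Section 4.4.2 (Exclusion Criteria) has one relevant entry: "Current use of other smoking cessation aids". It is a condition for entering the trial.

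Section 3.1 says that each participant's "involvement will last 26 weeks", with the last visit at Week 26. Section 3.3 lists as a secondary endpoint: "Proportion of participants achieving 7-day point prevalence abstinence at end of treatment, Week 3, Week 5, Week 9, Week 13, and Week 26". The same section adds prolonged and continuous abstinence at Weeks 13 and 26. Section 7.2 includes Week 26 among the time points of the mixed logistic model.

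Section 5.6 also says that concomitant "medications and therapies will be verified with research participants at each study visit", and Section 6.1 lists the concomitant medication log at Weeks 13 and 26.

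**The concern.** The protocol gives two lengths for the same study, and the shorter one is attached to an instruction that sites pass on to participants. Section 5.6 does not say that the request stops at Week 13 of a longer study; it treats 13 weeks as the whole study. The cross-reference to 4.4.2 does not help site staff, because that section contains no on-study request and no duration.

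What is at stake is the interpretation of the Week 26 abstinence results. Section 5.6 gives its own reason for the request, which is consistency with trials that excluded other cessation treatment. That reason applies at Week 26 as much as at Week 13. If drugs may be started in the second half, Week 26 abstinence may reflect TMS, a later drug, or both. A one-arm trial has no comparison group in which such late drug use would also appear.

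**Working it through.** This is mainly a comparison of texts and a timeline. The only calculation is a sense of scale.

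**1. Length of the study.** Stated in 5.6: 13 weeks. By Section 3.1 and the schedule in 6.2: 26 weeks. The figure in 5.6 cannot be reproduced from the schedule. No other section describes a 13-week study or extends the request.

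**2. Period not covered.** 26 − 13 = 13 weeks (Weeks 14 to 26), and 13/26 = 50%.

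**3. Point-prevalence time points.** End of treatment and Weeks 3, 5, 9 and 13 fall within 13 weeks: 5 of 6. Week 26 does not: 1 of 6. Its 7-day window opens at about Week 25, which is 25 − 13 = 12 weeks after the request ends.

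**4. Prolonged and continuous abstinence at Week 26.** Section 6.1 starts the prolonged window at the end of treatment and the continuous window at the target quit day in Week 1; both end at Week 26. Two cases differ:
- A participant still smoking after treatment who first quits after Week 13 meets neither definition, with or without a drug.
- A participant abstinent to Week 13 who then starts a drug to avoid relapse can meet both. Weeks 14 to 26 of both windows lie outside the request.

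**5. Do other rules close the gap?** The relevant ground for withdrawal in 4.7.1 is that a participant "Meets an exclusion criterion (either newly developed or not previously recognized) related to safety that precludes further treatment". Starting a cessation drug is not in itself a safety criterion. Section 7.2 analyses abstinence "including all participants who received at least one TMS session, regardless of treatment completion". A participant who starts a drug in, say, Week 15 therefore stays in the trial and in the analysis, and can count as abstinent at Week 26.

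**6. Scale, as a simple proportion.** This takes 40 treated as an upper bound, because Section 3.1 expects some of the 40 enrolled not to start treatment, and 30 as the target number of completers.
- One participant: 1/40 = 2.5 points; 1/30 = 3.3 points.
- Two participants: 2/40 = 5.0 points; 2/30 = 6.7 points.

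For comparison, exact (Clopper-Pearson) 95% intervals at assumed Week 26 rates of 20, 30 and 50%. The protocol gives no expected rate for this regimen, so these rates are assumptions.

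| Assumed rate | n = 40 | n = 30 |
|---|---|---|
| 20% | 9.1 to 35.6% | 7.7 to 38.6% |
| 30% | 16.6 to 46.5% | 14.7 to 49.4% |
| 50% | 33.8 to 66.2% | 31.3 to 68.7% |

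The intervals are about 27 to 32 points wide with 40 and 31 to 37 with 30. A shift of one or two participants is well inside that. The planned estimate comes from a mixed logistic model, so these shifts show scale only and are not the shift in that estimate.

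**The case against.** The strongest reply is that Week 13 may be a deliberate end. It is a scheduled visit and the 3-month abstinence assessment, and ending the request there would let relapsed smokers seek treatment. This is a fair reason and the protocol does not rule it out. But the text does not say it, and even then 13 weeks would be the wrong length for the study. The remedy must therefore allow for either intention.

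A second reply is that the 13-week wording does not itself create the counting problem. The request is only an ask. A participant who starts a drug at Week 6 against it would also stay in the analysis and could count as abstinent at Weeks 9 and 13. This stands: correcting the period does not settle how drug-aided abstinence is counted at any visit. What the wording adds is that, after Week 13, starting a drug is not even a departure from the request.

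A third reply is that handling such participants belongs in a statistical analysis plan, which is not at hand. This also stands, so the absence of a counting rule from the protocol is not part of this point. The length of the request is a protocol instruction, and the protocol states it inconsistently.

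A reader might infer that the Week 26 rate will be too high. The documents do not support that. They give no rate of late drug use, and a participant using nicotine replacement may fail the urine cotinine check (200 ng/mL) and count as not abstinent, so the net direction is unknown. Nor can one infer that the trial's main result is in doubt: tolerability, acceptability, retention and adherence do not depend on this request.

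**Conclusion.** The inconsistency is real and certain as a matter of text: 13 weeks in 5.6 against 26 weeks in 3.1, with a cross-reference that does not resolve it. As written, cessation drugs may be started in Weeks 14 to 26. The Week 26 abstinence outcomes can then partly reflect permitted medication: point prevalence generally, and prolonged or continuous abstinence in participants already abstinent at Week 13.

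The consequence is minor. It concerns secondary endpoints at one visit in a feasibility pilot, and one or two participants would move a simple proportion by 2.5 to 6.7 points, which is within sampling error at this sample size. That range assumes 30 to 40 treated participants and an invented count of one or two; with fewer treated, each participant weighs more. How many would start a drug, and in which direction the result would move, cannot be derived from the protocol.

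**What to change.** In Section 5.6, give the study length as 26 weeks so that the request runs to the Week 26 visit, and state the request there in full instead of pointing to 4.4.2. If an end at Week 13 is intended so that relapsed smokers can seek treatment, say so and give the reason.

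In either case, report the Week 26 abstinence outcomes (point prevalence, prolonged and continuous) as observed, and again with participants whose medication log shows a cessation drug started after treatment counted as not abstinent. This addresses the counting at Week 26, which the change of wording alone does not.

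The cost is a sentence or two in 5.6 and one extra tabulation from a log already scheduled at Week 26. There are two downsides: the second set of rates may be lower, and a request running to Week 26 asks relapsed smokers to hold off medication for 13 weeks longer.
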